## 2.3 Rationale

Lymphoseek is the first FDA-approved receptor-targeted lymphatic mapping agent. Lymphoseek is a small synthetic molecule that carries multiple mannose residues and is specifically recognized by the mannose receptor which is highly enriched on the cell surface of macrophages and dendritic cells. High-affinity receptor binding, guarantees 100% extraction of the agent by the lymph node and abrogates tracer leakage and distal lymph node accumulation. In addition to its SLN superior accumulation as a consequence of specific lymph node uptake, through rapid interstitial passive diffusion and lymph drainage, Lymphoseek clears the injection site within 10 minutes and accumulates in sentinel lymph nodes where it remains bound for up to 30 hours.

We hypothesize that through these different mechanisms of action, the implementation of Lymphoseek into our sentinel lymph node algorithm for endometrial cancer will significantly improve bilateral and overall detection rates. The preoperative imaging using SPECT/CT and not only planar lymphoscintigraphy will furthermore provide critical preoperative information about the location of sentinel lymph nodes, which is especially important in scenarios where the sentinel lymph node maps to atypical locations such as the pre-sacral and para-aortic regions [30]. The true incidence of these less frequent sentinel lymph node locations is unknown, since they cannot be reliably assessed using thus-far available tracers including nonspecific radioactive

tracers, or fluorescent or non-fluorescent dyes. With the a-priori knowledge of the preoperative SPECT/CT imaging, the intraoperative use of Indocyanine Green will continue to visually guide the surgeon in situ. A laparoscopic gamma counter will help confirm thus identified sentinel lymph nodes and the removal in their entirety. We believe that the proposed combined approach of Lymphoseek and Indocyanine Green will improve sentinel lymph node detection rates and thereby decrease the surgical morbidity associated with a complete lymphadenectomy.

## **2.4 Study Design**

This is an open-label, single-center single-group prospective diagnostic trial.

## **3. PARTICIPANT SELECTION AND ENROLLMENT PROCEDURES**

Refer to the Participant Eligibility Checklist in Appendix A.

### **3.1 Inclusion Criteria**

- The patient has histological diagnosis of cancer of the endometrium of any histology or grade.
- The patient should have received no prior treatment for her endometrial cancer.
- The patient has clinically uterine confined disease.
- The patient is a candidate for minimal invasive surgery, with sentinel lymph node assessment with IC-GREEN planned as part of standard of care.
- The patient has an Eastern Cooperative Group (ECOG) performance status of 0-2.
- If age less than or equal to 55 years, the patient has a negative pregnancy test within 72 hours before administration of Lymphoseek, has been surgically sterilized, or has been postmenopausal for at least 1 year.
- The patient has provided written informed consent.
- The patient is at least 18 years of age at the time of consent.

### **3.2 Exclusion Criteria**

- The patient has clinical or radiological evidence of metastatic disease.
- The patient has a known hypersensitivity to Indocyanine Green and/or Lymphoseek.
- The patient has a history of a prior loop electrosurgical excision procedure (LEEP) or cone procedure performed on her cervix.
- The patient has participated in another investigational drug study within 30 days of scheduled surgery.
- The patient has an iodine allergy.
- The patient is pregnant or lactating.

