## 2.2 Study agent - Lymphoseek

(99m)Tc-diethylenetriaminepentaacetic acid (DTPA)--mannosyl-dextran (Lymphoseek) was first synthesized and described in 2001 by Vera et al. [26]. In contrast to all other dyes and tracers used in sentinel lymph node detection, this synthetic radiotracer was specifically designed for sentinel lymph node mapping. The molecule has a molecular weight of 35.8 kDa and a diameter of 7.1 nm and consists of a dextran backbone and 8 DTPA groups. The DTPA groups are used for the chelation of Tc 99m Technetium.

55 mannose residues are covalently bound to the dextran backbone. These 55 mannose residues provide high receptor affinity to the mannose receptor CD 206 which is highly enriched on the surface of macrophages and dendritic cells. Lymphoseek has a dissociation constant of 0.12 nmol/L. This low dissociation constant ensures the effective uptake of the agent by the lymph node and improved retention and thus a lower distal lymph node accumulation than seen for the nonreceptor-targeted filtered Tc 99m-sulfur colloid [27]. Accordingly, Lymphoseek accumulates in fewer lymph nodes with higher specificity [28].

Furthermore, the dextran backbone guarantees rapid injection site clearance which entails the rapid diffusion from the injection site through lymph and blood vessels. In fact, neutral dextrans show an interstitial diffusion coefficient 10-fold greater than for proteins of the same hydrodynamic radius, a property which has been attributed to hydrophilicity and flexibility of the dextrans and the absence of charge. A radiotracer that clears more rapidly from the injection site, even if the tracer delivers equal activity to the sentinel node, will provide higher signal-to-noise ratio by reducing the unspecific background and thus better a detection rate than an agent with slower clearance [27].

While Lymphoseek has been FDA-approved in breast cancer, melanoma, and head and neck cancer [29], no published studies exist for the use of Lymphoseek in endometrial cancer.

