#### 4.2 Alternatives

Injection with Indocyanine Green alone for sentinel lymph node mapping and biopsy in clinical uterine confined endometrial cancer is currently considered standard of care.

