## **7. ADVERSE EVENTS AND REPORTING PROCEDURES**

### **7.1 Potential Adverse Events**

#### **7.1.1 Potential Adverse Events associated with Lymphoseek**

The most common adverse reactions (incidence <1%) are injection site irritation and/or pain. In open label, single-arm clinical trials, 553 patients with either breast cancer, melanoma, or squamous cell carcinoma of the oral cavity, skin, lip received Lymphoseek. No patient experienced serious adverse reaction. Injection site irritation (0.7%) and pain (0.2%) were reported [29].

Lymphoseek may pose a risk of hypersensitivity reactions due to its chemical similarity to dextran. No hypersensitivity reactions have been reported in the literature.

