### IV. Inclusion/Exclusion Criteria

Inclusion Criteria (From IRB approved protocol)	Yes	No	Supporting Documentation*
1. Age 18 or older			
2. Patient has histological diagnosis of cancer of the endometrium.			
3. Patient should have received no prior treatment.			
4. Patient has a clinical negative node status at study entry.			
5. Patient is a candidate for minimal invasive surgery with lymph node assessment.			
6. Eastern Cooperative Group (ECOG)			

performance status of 0-2			
7. If age less than or equal to 55 years, the patient has a negative pregnancy test within 72 hours before administration of Lymphoseek, has been surgically sterilized, or has been postmenopausal for at least 1 year.			
8. Willing and able to provide a written informed consent document for the trial.			
Exclusion Criteria (From IRB approved protocol)			
1. Patient has participated in another investigational drug study within 30 days of scheduled surgery.			
2. Patient has clinical or radiological evidence of metastatic disease.			
3. Patient has a history of a prior loop electrosurgical excision procedure (LEEP) or cone procedure performed on her cervix.			
4. Patient has a history of previous abdominal retroperitoneal surgery or abdominal/pelvic lymphadenectomy.			
5. Patient has a known hypersensitivity to Indocyanine Green and/or Lymphoseek.			
6. The patient has an iodine allergy			
7. The patient is pregnant or lactating.			

\*All subject files must include supporting documentation to confirm subject eligibility.

The method of confirmation can include, but is not limited to, laboratory test results, radiology test results, subject self-report, and medical record review.

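### The protocol ties Lymphoseek's hypersensitivity risk to dextran, but neither section 3.2 nor the eligibility checklist excludes a woman with a known dextran reaction

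*Combined protocol and SAP*

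**What the plan says.** Section 2.2 states that the Lymphoseek molecule "consists of a dextran backbone and 8 DTPA groups". Section 7.1.1 draws the safety consequence: "Lymphoseek may pose a risk of hypersensitivity reactions due to its chemical similarity to dextran". It then gives the evidence to date: "No hypersensitivity reactions have been reported in the literature", and, for 553 patients treated in open-label single-arm trials, "No patient experienced serious adverse reaction".

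Section 3.2 has two allergy exclusions: "The patient has a known hypersensitivity to Indocyanine Green and/or Lymphoseek" and "The patient has an iodine allergy". The Appendix A checklist repeats them as exclusions 5 and 6, the former worded "Patient has a known hypersensitivity to Indocyanine Green and/or Lymphoseek".

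Section 4 has eligibility decided by the inclusion and exclusion criteria. Section 4.2 gives the standard of care outside the study: "Injection with Indocyanine Green alone for sentinel lymph node mapping and biopsy".

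**The concern.** The safety section names one mechanism by which Lymphoseek might cause hypersensitivity, and the eligibility section does not screen for the history that corresponds to it. Excluding known hypersensitivity to Lymphoseek does little here. A woman must have received the agent to be known to react to it, and section 2.2 gives its approved uses as breast cancer, melanoma and head and neck cancer, with no published use in endometrial cancer. It is reasonable to infer that few candidates will have had it before.

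What is at stake is participant safety. Since Indocyanine Green alone is standard care, Lymphoseek is the agent given only because of the study, and a woman would meet this risk only by enrolling. Safety of concurrent use is also a stated secondary objective (section 1.2). No bias in the detection rate is alleged.

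**Working it through.** **Where dextran appears.** Apart from a reference title, dextran is mentioned only in section 2.2 (structure and diffusion) and section 7.1.1 (the warning). It is absent from sections 3.1, 3.2, 4, 4.1 and 8 and from the Appendix A criteria.

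**Whether another rule would stop the injection.**

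| Provision | Does it exclude a woman with a past dextran reaction? |
|---|---|
| 3.2 and checklist 5: hypersensitivity to either agent | No, if she has never had Lymphoseek |
| 3.2 and checklist 6: iodine | No |
| 4: eligibility by the listed criteria | No; the list has no investigator-discretion exclusion |
| 4.1: removal on the investigator's opinion | No; it covers an adverse event, laboratory abnormality or intercurrent illness, not a past allergy |
| 8: pre-study medical history | No; no dextran question is specified and no criterion acts on the answer |
| 4 and 6: observation, then epinephrine, antihistamines and corticosteroids | No; these act after exposure |

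**How often it might arise.** The documents give no frequency of dextran allergy, so the range below is an assumption. With n = 30 (section 11.6.2) and frequency f, the expected number is 30f and the chance of at least one is 1 − (1 − f)^30.

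- f = 0.1%: 30 × 0.001 = 0.03 expected; 1 − 0.999^30 = 0.0296, or 3.0%.
- f = 1%: 30 × 0.01 = 0.3 expected; 1 − 0.99^30 = 0.2603, or 26.0%.

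These are chances of enrolling such a woman, not of a reaction.

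**What the 553 recipients show.** With zero serious adverse reactions in 553:

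- one-sided 95% upper limit: 1 − 0.05^(1/553) = 0.0054, or 0.54%;
- exact two-sided 95% upper limit: 1 − 0.025^(1/553) = 0.0066, or 0.66%.

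Both limits describe recipients in general. The documents do not say whether any of the 553 had a dextran allergy, so neither limit can be carried over to such women.

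**Effect on the design.** The plan gives no figure on this point. Its design figures in section 11.6.2 reproduce: with 30 patients and at least 24 bilateral detections required, the exact binomial tail is 0.607 at a true rate of 80% and 0.133 at 69%, matching the stated 61% and 13%. A dextran exclusion leaves them unchanged.

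**The case against.** The strongest reply is that the decisive step is the reviewer's. Section 7.1.1 describes a possible property of the agent in any recipient. It does not say that a prior dextran reaction raises the risk or is a contraindication, so no two sections contradict each other. The record it cites is reassuring. The iodine exclusion is not a close parallel either: section 7.1.2 says Indocyanine Green reactions have been reported, and section 5.2 says the product contains sodium iodide.

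There are also people in the way. Appendix A has the coordinator, the treating physician and an independent reviewer verify eligibility, and section 5.1.1 requires specifically trained physicians. A clinician might read hypersensitivity to Lymphoseek as covering its dextran component.

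Finally, the frequency range is assumed, the 26.0% comes entirely from its upper end, and the women with a known reaction, whom the exclusion would catch, may be fewer than all who are allergic.

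Much of this stands. The higher risk is inferred, the risk is theoretical, the iodine line shows only that a related allergen can be screened in one line, and the figures give scale rather than proof. Clinical judgement makes an unconsidered injection less likely. It does not close the gap: the verification step checks the listed criteria, dextran is not among them, and the component reading is not written down.

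**Conclusion.** The concern holds. Followed as written, the exclusions admit the patient to whom the protocol's own warning points, and no other rule bars her from the injection. Existing observation and treatment would limit the harm of a reaction but not prevent the exposure.

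The size is small: a rare, theoretical safety risk, with 0.03 to 0.3 such women expected among 30 if dextran allergy has a frequency of 0.1% to 1%. The conclusion rests on that assumed range and on the inference that similarity to dextran matters most to women who have reacted to it. Neither can be confirmed from the documents. Consent pages were not available, so any dextran wording there could not be checked. The change should be made because it is cheap and concerns a study-only agent. It does not bear on the primary analysis or the rule of 24 in 30.

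**What to change.** In section 3.2 and in checklist exclusion 5 of Appendix A, add dextran as a third named substance beside Indocyanine Green and Lymphoseek. In the pre-study medical history that section 8 already schedules, add a question on prior reactions to dextran.

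The cost is one phrase in two places and one question, with no new test or visit. The downside is that an occasional otherwise eligible woman is not enrolled: 0.03 to 0.3 expected among 30 under the assumed frequencies.

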### **3.3 Informed Consent Process**

All participants must be provided a consent form describing the study with sufficient

information for participants to make an informed decision regarding their participation. Participants must sign the IRB approved informed consent prior to participation in any study specific procedure. The participant must receive a copy of the signed and dated consent document. The original signed copy of the consent document must be retained in the medical record or research file.

### **3.4 Study Timeline**

#### **Primary Completion:**

The study will reach primary completion 12 months from the time the study opens to accrual.

#### **Study Completion:**

The study will reach study completion 24 months from the time the study opens to accrual.

## **4. TREATMENT PLAN**

In this study, the patient will receive cervical injections of Lymphoseek 1 – 24 hours prior to surgery and subsequent SPECT/CT imaging preoperatively. Intraoperatively, following anesthesia induction, Indocyanine Green will be injected into the uterine cervix. Using near-infrared imaging, efferent lymphatic vessels and lymph nodes will be visualized and confirmed by detected radioactivity using a laparoscopic gamma counter. The preoperatively obtained SPECT/CT images will help guide the surgery. The laparoscopic gamma counter will confirm that sentinel lymph node tissue was removed by recording gamma counts before and after lymph node removal.

Subject participation in this study comprises the following:

- Screening**

- Screening begins after informed consent is obtained.
- The screening window is Day 1 to Day 42 after signing of informed consent.
- Screening assesses the subject's eligibility to participate as determined by inclusion/ exclusion criteria.

- Sentinel lymph node assessment**

- Preoperatively, 1 - 24 hrs prior to surgery, the patient will receive in the nuclear medicine suite of Stanford Hospital injections of 0.125 mCi or 0.5 mCi mL each Lymphoseek into the uterine cervix at 3, 6, 9, and 12 o'clock. Then, the patient will undergo SPECT/ CT imaging. Immediate and delayed static planar images will be obtained with and without a transmission source. SPECT-CT of the abdomen and pelvis will be obtained for further characterization. The imaging process will take approximately 1 hour.

- The patient will undergo minimally invasive endometrial cancer surgery. The SPECT/ CT images will be available for review to the surgeon prior to the start of the surgery.
- In the operating room, following anesthesia induction, the uterine cervix of the patient will be injected with about 2.0 mL total of Indocyanine Green. The surgery will start with the identification and dissection of sentinel lymph nodes.
- **Follow up (duration of the study)**
  - The patient will be observed preoperatively after Lymphoseek injection in the nuclear medicine suite and postoperatively in the recovery room for possible allergic reactions or any other adverse events.
  - There will be a routine postoperative visit to be performed that will be conducted in person or remotely via telemedicine between 14-28 days after surgery. This will be a telemedicine visit where the patient will collect the weight, vitals and the physical examination and AE evaluation will be conducted by assistance of the physician remotely. There are no risks to participants for missing any follow up procedures that can't be conducted remotely.

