## PROTOCOL SYNOPSIS

TITLE	Concurrent use of Lymphoseek and Indocyanine Green for sentinel lymph node detection in endometrial cancer – a prospective study
STUDY PHASE	Feasibility
INDICATION	Sentinel lymph node sampling in clinically uterine confined early-stage endometrial cancer
INVESTIGATIONAL PRODUCT OR PROCEDURE	Concurrent use of Lymphoseek and Indocyanine Green in minimally invasive surgery
PRIMARY OBJECTIVE(S)	To determine the detection rate of bilateral sentinel lymph nodes with the concurrent use of Lymphoseek and Indocyanine Green as compared to each agent alone.
SECONDARY OBJECTIVE(S)	
(1) To determine the overall detection rate of sentinel lymph nodes with concurrent use of Lymphoseek and Indocyanine Green
 
(2) To determine location and number of Lymphoseek-positive sentinel lymph nodes preoperatively by single-photon emission computed tomography (SPECT/CT imaging) and intraoperatively by a laparoscopic handheld gamma detection
 
(3) To determine the location and number of Indocyanine Green-positive sentinel lymph nodes by intraoperative infrared fluorescent imaging
 
(4) To determine the concordance of Lymphoseek-positive sentinel lymph nodes with intraoperatively detected Indocyanine Green-positive sentinel lymph nodes, and vice versa, the concordance of Indocyanine Green-positive sentinel lymph nodes with Lymphoseek-positive sentinel lymph nodes.
 
(5) To assess the safety of the concurrent use of Lymphoseek and Indocyanine Green

TREATMENT SUMMARY	
Sentinel lymph node assessment
 
 
- Preoperatively, within 24 hours prior to surgery, the subject will receive in the nuclear medicine suite of Stanford Hospital injections of 0.125 mCi or 0.5 mCi each Lymphoseek into the uterine cervix at 3, 6, 9, and 12 o'clock. Immediate and delayed static planar images will be obtained with and without a transmission source. SPECT-CT of the abdomen and pelvis will be obtained for further characterization.
 
- Subjects will then undergo minimally invasive endometrial cancer surgery. The SPECT/ CT images will be available for review to the surgeon prior to the start of the surgery.
 
- In the operating room, following anesthesia induction, the uterine cervix will be injected with 0.5 mL each of Indocyanine Green at positions of 3, 6, 9, and 12 o'clock.
 
- The surgery will start with the identification and dissection of
 

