	sentinel lymph nodes using near infrared imaging and the gamma probe.
SAMPLE SIZE	30 patients over 1 year
STATISTICAL CONSIDERATIONS	
The analysis population will include all patients who complete the study procedures specified above. We do not expect missing data or loss-to-follow up since the outcome is ascertained at the time of surgery. Patients who do not adhere to the study treatment plan of both injections, SPECT/CT and surgery with sentinel lymph node assessment will not be included in the analysis population.
 
To address our primary objective, we plan to enroll 30 patients with concurrent use of lymphoseek and indocyanine green over 1 year. The primary analysis is the calculation of the bilateral SLN detection rate which will be calculated as the number of patients with bilateral SLN detection divided by the total number of patients.
 
With 30 participants and assuming a true bilateral detection rate of 80%, the probability of correctly concluding that our approach has an acceptable bilateral detection rate (i.e., 24 patients being detected with bilateral SLNs) is 61%. The probability of incorrectly concluding this (assuming that the true detection rate is 69%) is low at 13%. We will deem the approach used in this study promising if we observe a bilateral detection rate of at least 80%.

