### **11.5.2 Analysis Plan**

Descriptive statistics will be used to analyze the secondary outcomes. The overall detection rate of sentinel lymph nodes will be calculated as the number of patients with overall SLN detection divided by the total number of patients. To assess the safety of the concurrent use Lymphoseek and Indocyanine Green, we will calculate the number and rate of adverse events. We will describe the location and number of Lymphoseek-positive SLNs by method of detection (pre-operative or intraoperative). We will calculate the number of patients with SLNs found by Lymphoseek and by Indocyanine Green and conduct a McNemar's test (or mid- $p$  McNemar's test) to determine the concordance of Lymphoseek-positive and Indocyanine Green-positive sentinel lymph nodes.

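### The ICG result is read with SPECT/CT guidance and no rule to record it first, so the trial cannot give an ICG-alone rate or answer the synopsis comparison with each agent alone

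*Combined protocol and SAP*

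**What the plan says.** **Order of information.** Lymphoseek is injected and imaged before surgery. Section 4 states: "The SPECT/ CT images will be available for review to the surgeon prior to the start of the surgery". It adds: "The preoperatively obtained SPECT/CT images will help guide the surgery". Section 2.3 gives the intent: "With the a-priori knowledge of the preoperative SPECT/CT imaging, the intraoperative use of Indocyanine Green will continue to visually guide the surgeon in situ". ICG is injected only after anesthesia induction, so the images can be known before any near-infrared reading.

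**Intraoperative step.** The synopsis has the surgeon identify and dissect "sentinel lymph nodes using near infrared imaging and the gamma probe". Section 4 puts the near-infrared view first: "lymph nodes will be visualized and confirmed by detected radioactivity using a laparoscopic gamma counter". No section blinds the surgeon to the scan, provides an independent reader, or requires the near-infrared result to be recorded before the probe is used.

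**Design.** Section 2.4: "This is an open-label, single-center single-group prospective diagnostic trial". There is no ICG-only group.

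**Agent-specific results that are planned or promised.**
- The synopsis states the primary objective as the bilateral detection rate "with the concurrent use of Lymphoseek and Indocyanine Green as compared to each agent alone". Section 1.1 states the same objective without the comparison.
- Section 9.2(3) makes location and number of ICG-detected nodes a separate outcome. It counts a node only if near-infrared found it and the gamma device did not.
- Section 11.5.2: "We will calculate the number of patients with SLNs found by Lymphoseek and by Indocyanine Green", followed by McNemar's test (or its mid-p form) as the measure of concordance.

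**The concern.** A rate for one agent alone, or a paired comparison of two agents, needs each reading to be made without help from the other. Here the Lymphoseek scan may already have told the surgeon where to look when the near-infrared reading is made. A node called ICG-positive may have been found for that reason. Section 2.3 expects the scan to matter most for nodes in atypical places, and those are nodes an unguided search could miss.

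If guidance works as the sponsor hopes, some patients whom ICG alone would have missed are recorded as positive by both agents. That raises the ICG rate, raises apparent agreement, and shrinks the visible contribution of Lymphoseek in the secondary results. It cannot be undone afterwards, because an unguided reading that was never recorded cannot be recovered from the data.

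**Working it through.** **1. The plan's own figures (11.6.2).** With n = 30 and success defined as at least 24 bilateral detections:
- P(X ≥ 24 | p = 0.80) = 60.7% (plan: 61%)
- P(X ≥ 24 | p = 0.69) = 13.3% (plan: 13%)
- exact 95% interval for 24/30 = 61.4% to 92.3% (plan: 61% to 92%)

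All three reproduce. None depends on how a detection is attributed between agents, because 9.1 counts a side as detected if SPECT/CT, near-infrared or the gamma probe finds a node. A patient moved from Lymphoseek-only to positive by both was already a success.

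**2. Which patients guidance can convert.** Inputs: ICG bilateral rate 69% (2.1, institutional data) and assumed combined bilateral rate 80% (11.6.2). Treating 69% as the true ICG-alone rate in this trial is an assumption.
- Missed bilaterally by ICG alone: 100 − 69 = 31 points.
- Missed bilaterally by every method: 100 − 80 = 20 points. For these patients Lymphoseek showed no node on the missing side, so it could not guide anyone there.
- Convertible: 31 − 20 = 11 points, or 0.11 × 30 = 3.3 patients. They are bilateral only because Lymphoseek supplies at least one side.

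**3. Illustration.** Let g be the share of the convertible group that guidance turns into recorded ICG detections.
- Recorded ICG = 0.69 + g × 0.11
- Visible gain = 0.80 − recorded ICG = 0.11 × (1 − g)

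| g | Recorded ICG | Visible gain (points) | Patients of 30 |
|---|---|---|---|
| 0 | 69.0% | 11.0 | 3.3 |
| 0.10 | 70.1% | 9.9 | 3.0 |
| 0.25 | 71.8% | 8.3 | 2.5 |
| 0.50 | 74.5% | 5.5 | 1.7 |
| 1 | 80.0% | 0 | 0 |

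The documents give no value for g. The table shows a range, not an estimate.

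**4. What the table does not size.** The 69% and 80% are bilateral rates. Section 11.5.2 counts patients with nodes found by each agent and does not say bilaterally; the any-side ICG rate in 2.1 is 88%. The table therefore does not quantify the McNemar test.

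**5. A pull in the other direction.** Read literally, 9.2(3) drops every node that the gamma probe also found. For scale, take bilateral detection by Lymphoseek alone as 73% to 80%. That is the colloid range in 2.1.1, used only as a stand-in. Treat every Lymphoseek detection as gamma-positive.
- At 73%: both agents = 73 − 11 = 62%; ICG without Lymphoseek = 69 − 62 = 7%.
- At 80%: both agents = 80 − 11 = 69%; ICG without Lymphoseek = 69 − 69 = 0%.

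So the literal definition would depress the ICG count, while guidance would raise it.

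**The case against.** The strongest reply is that image-guided ICG is the intervention. Section 2.3 says so, and withholding the images during the first search would change the procedure under study. This stands. It does not justify presenting the guided reading as ICG alone.

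Second, the planned judgement of benefit is the combined rate against an 80% threshold set from the institution's 69% (11.4.2, 11.6.3). That 69% is prior institutional data and cannot be altered by guidance in this trial. This also stands. A reader might infer that the contamination biases the primary result or hides the gain on which the trial is judged; 9.1 and 11.4.2 do not support that.

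Third, a reader might apply the conversion share to all 31 points of ICG misses. That overstates the effect: once the share passes 0.11 / 0.31 = 0.355, recorded ICG would exceed the combination, which the any-method definition in 9.1 rules out.

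Fourth, the gamma route is weaker than the SPECT/CT route. Section 4 describes a near-infrared view followed by gamma confirmation, not an ICG call prompted by the probe. What remains is that nothing requires the first reading to be recorded before the second.

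Finally, the documents say that the images are available and will help. They do not establish that every surgeon reviews them in every case.

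**Conclusion.** The point holds for the agent-specific results. As designed, 9.2(3) and the concordance and McNemar analysis in 11.5.2 measure SPECT/CT-guided ICG, and the comparison with each agent alone in the synopsis cannot be answered. Section 1.1 omits that comparison and section 11 plans no bilateral ICG-alone rate, so the synopsis and the body also need reconciling.

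The likely direction is to overstate ICG and its agreement with Lymphoseek, with the literal 9.2(3) definition working against this. The net size cannot be derived. If 69% and 80% are taken as true and 10% to 50% of the Lymphoseek-dependent patients are converted, the visible bilateral gain falls from 11 points to between 9.9 and 5.5. With about three such patients expected in 30, one or two guided detections change the picture. The primary outcome and its decision rule stand as written.

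**What to change.** 1. On the CRF, record the near-infrared result for each side before the gamma probe is used on that side. This follows the order that section 4 already describes. Record also whether SPECT/CT had been reviewed and which modality first located each node.
2. In 9.2(3) and 11.5.2, label the result SPECT/CT-guided ICG. Do not report it as ICG alone, and do not read the McNemar result as a comparison of independent agents.
3. Reconcile the primary objective in the synopsis with 1.1.

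Recording near-infrared before SPECT/CT review would give a cleaner ICG-alone rate. It alters the image-guided procedure, so it is an option for the sponsor to weigh and not a requirement of this point.

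The cost is a few CRF fields per side, some wording changes, and a more limited claim about ICG alone. The CRF fields must be in place before the surgeries they describe, since the order of detection cannot be reconstructed later.
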